15.2.2 MISSING DATA METHODS FOR SECONDARY EFFICACY VARIABLES

Last observation carried forward (LOCF) method will be adopted as imputation in the presence of at least one post-baseline observation if data is collected at multiple visits post baseline and is missing. Missing items in, Top 3 concerns score at baseline will be imputed with the mean baseline value of that item of all patients in the analysis population. There will be no imputation for MBAS, RCSS and Other Respiratory symptoms of RTT since only descriptive summary is presented.

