The mean rating of the caregiver-rated CIC at Week 24/endpoint will be compared between treatment groups using the Van Elteren test (a stratified Cochran Mantel Haenszel test with modified ridit scores). The following age strata will be considered in the analysis: <13 years and \geq 13 years. In addition to the above analysis, comparisons between treatments for the proportion of patients rated improved at Week 24 will be done using logistic regression.

Other Secondary Efficacy Outcomes

The analysis of the Caregiver Top 3 Concerns will be performed first, comparing the change from baseline in the total score on the VAS for each of the 3 symptoms identified as most concerning at baseline using an ANCOVA-LOCF analysis. The model will include treatment group and the baseline value along with age as covariates. Change will be estimated using the least-squares mean derived from the ANCOVA. Comparisons between treatment groups at Week 24 will be made using the difference in least-squares mean, 95% confidence interval (CI) and p-values from the ANCOVA model.

Descriptive statistics will be presented for the other secondary efficacy outcomes. The proportion of patients rated improved, as well as the mean score, on the Investigator-rated CGI-C at each of the scheduled visits will be presented. Actual values and the change from baseline in other secondary efficacy variables (Motor Behavioral Assessment Scale and subscales, other respiratory parameters, and RCSS) at all scheduled visits will be presented. An additional analysis of efficacy will be performed for patients with a sarizotan plasma concentration of >400 ng/mL.

Multiple Comparisons/ Multiplicity

The study level error rate will be controlled by following a sequential multiple testing procedure, where testing will begin with the primary efficacy endpoint. The effects of the high dose sarizotan versus placebo will be analyzed first for all parameters in a pre-specified sequence.

The sequence of testing will be as presented below:

- Percentage change from baseline in the number of apnea episodes,
- Mean rating of CIC,
- Mean change from baseline in the Top Three Concerns Total Score.

Initial 24-week Double-blind Treatment Period

The primary efficacy assessment for the study will be performed using data from the initial 24-week double-blind, placebo-controlled treatment period. A statistical “Win” will be claimed if the following results are obtained in the primary and key secondary efficacy analyses:

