The assumptions for the estimated standard deviation (SD) are based on limited data from a study by [Khwaja et al. \(2014\)](#), in RTT patients. There were only 5 patients with data reported for apnea index (for apnea episodes > 10 seconds). Pilot observational data collected using the BioRadio™ device in 26 patients with RTT indicated that the number of episodes of apnea may approach 60 per hour. Based on the range of 10-60 episodes per hour, ranges of 10-30, 10-45 and 10-60 apnea episodes per hour indicate SDs of 5.0, 8.75 and 12.5, respectively.

Sample sizes were computed to determine the number of patients required to detect a minimum difference in mean percent reduction of 20% (high dose sarizotan 30%, placebo 10%; see [Table 1](#)) and 10% (high dose sarizotan 20%, placebo 10%; see [Table 2](#)), based on differences between high dose sarizotan and placebo.

Table 1. Sample Size Estimates Assuming 90% Power and – 20% Difference

Parameter	1	2	3	4
Test significance level, α	0.050	0.050	0.050	0.050
1 or 2 sided test?	2	2	2	2
High Dose mean % Chg, μ_1	-30.00	- 30.00	- 30.00	-30.00
Placebo mean % Chg, μ_2	-10.00	-10.00	- 10.00	-10.00
Difference, $\mu_1 - \mu_2$	-20.00	-20.00	- 20.00	-20.00
Common St. Dev., σ	12.50	15.00	20.00	25.00
Effect size, $\delta = \mu_1 - \mu_2 / \sigma$	1.60	1.33	1.00	0.80
Power (%)	90	90	90	90
n per group	10	13	23	34

Document: \\ieedc-vnasc01\BIOSdata\Newron\Sarizotan\PXA76395\Biostatistics\Documentation\SAP
 Author: [name] Version Number: V2
 Version Date: [30March2020]
 Template No: CS_TP_BS016 – Revision 4 Reference: CS_WI_BS005
 Effective Date: 01Apr2016

Table 2. Sample Size Estimates Assuming 90% Power and – 10% Difference

Parameter	1	2	3	4
Test significance level, α	0.050	0.050	0.050	0.050
1 or 2 sided test?	2	2	2	2
High Dose mean % Chg, μ_1	-20.00	- 20.00	- 20.00	-20.00
Placebo mean % Chg, μ_2	-10.00	-10.00	-10.00	-10.00
Difference, $\mu_1 - \mu_2$	-10.00	-10.00	-10.00	-10.00
Common St. Dev., σ	20.00	12.50	8.75	5.00
Effect size, $\delta = \mu_1 - \mu_2 / \sigma$	0.50	0.80	1.14	2.00
Power (%)	90	90	90	90
n per group	86	34	18	7

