Sample sizes of 23 or 34 in each treatment group would have 90% power to detect a difference in mean percent reduction of -20% or -10%, respectively, assuming a common SD of 20 (for the 20% reduction) and 12.5 (for the 10% reduction), using a two group t-test with a 0.050 two-sided significance level. Assuming an attrition rate of 25% (7 or 9 patients) per group, a total of 30 or 43 patients would need to be enrolled in each group to get 23 or 34 patients completing the study. As this is the first large-scale study evaluating the effect of sarizotan on respiratory symptoms in patients with RTT, a conservative estimate of 10% reduction in apnea episodes was used to estimate the sample size required, i.e. approximately 43 patients per group.

Mode of dose: Oral (capsules), or as a solution either orally (for patients with swallowing difficulties) or through a gastrostomy tube (G-tube)

Blinding:

A randomization number corresponding to the treatment assignment was assigned to each randomized subject using an Interactive Web Response System (IWRS), and was registered in the subject’s files for identification. If it was necessary to break the blind during the double-blind period for reasons of safety, the Investigator was able to break the blind using the IWRS. The Investigator was asked to inform the Sponsor and their representative of this as soon as possible and to provide a reason for the unblinding.

Document:	\\ieedc-vnasc01\BIOSdata\Newron\Sarizotan\PXA76395\Biostatistics\Documentation\SAP		
Author:	[name]	Version Number:	V2
		Version Date:	[30March2020]
Template No:	CS_TP_BS016 – Revision 4	Reference:	CS_WI_BS005
Effective Date:	01Apr2016		

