15.1.4 KEY SECONDARY EFFICACY VARIABLE

The key secondary efficacy outcome was the difference between sarizotan and placebo on the Caregiver-rated Impression of Change (CIC) from baseline, a 7-point Likert-type scale for which ratings range from 1 = very much improved to 7 = very much worse, with 4 = no change. The key secondary efficacy analysis will be performed for the ITT population.

Summary statistics for CIC mean rating scores will be provided by visit and treatment group.

The mean rating of the caregiver-rated CIC at Week 24 LOCF will be compared between treatment groups using the Van Elteren test (a stratified Cochran Mantel Haenszel test with modified ridit scores). The following age strata will be considered in the analysis:

<13 years

>=13 years

Improvement on the CIC (i.e. Responder) will be defined as a Likert scale score of 1 (very

Document:	\\ieedc-vnasc01\BIOSdata\Newron\Sarizotan\PXA76395\Biostatistics\Documentation\SAP	Version Number:	V2
Author:	[name]	Version Date:	[30March2020]

Template No: CS_TP_BS016 – Revision 4
 Effective Date: 01Apr2016

Reference: CS_WI_BS005

much improved), 2 (much improved) or 3 (minimally improved). The proportion of patients with a rating of improvement in the CIC (n, count, and percent) will be presented at post-baseline visits by treatment group.

In addition to the above analysis, comparisons between treatments for the proportion of responders at Week 24 LOCF will be done using logistic regression. The logistic regression model will include treatment group and age. For the treatment comparison, an estimate of the odds ratio, corresponding Wald 95% CI and chi-square p-value will be presented.

Additionally, graphical presentation will be provided for the proportion of responders at Week 24.

In accordance with the original protocol (dated 27 October 2015, Section, page 70, Section 15.2.6) and the amended protocol (version 11.0, incorporating protocol Amendment 10, dated 29 November 2018, page 100, Section 15.2.6) as referred to in the FDA minutes of the meeting of February 5, 2020 issued by the FDA March 4, 2020, the Sponsor has reverted to using the “win” criteria referred to in these sections, as directed by FDA. A statistical “Win” will be claimed if the following results are obtained in the primary and key secondary efficacy analyses:

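### CIC and Top 3 Concerns are tested on LOCF data with no missing-data sensitivity analysis. LOCF biases the Week 24 difference if the effect changes over time, or if dropout is unequal and the outcome has a time trend.

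*SAP*

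**What the plan says.** SAP 15.2.2 sets the general rule for secondary endpoints: "Last observation carried forward (LOCF) method will be adopted as imputation in the presence of at least one post-baseline observation". SAP 15.1.4 applies it to the key secondary endpoint: "The mean rating of the caregiver-rated CIC at Week 24 LOCF will be compared between treatment groups using the Van Elteren test". The CIC responder logistic regression in the same section also uses Week 24 LOCF. For Top 3 Concerns, SAP 15.2 specifies the ITT population with LOCF, and Protocol 15.2.6 describes the comparison as made "using an ANCOVA-LOCF analysis".

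SAP 7.4 places CIC second and Top 3 third in the testing sequence. The win rule in SAP 15.1.4 needs a significant primary result plus a CIC difference in the right direction.

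Dropout is expected. SAP 3.1 plans the sample size "Assuming an attrition rate of 25% (7 or 9 patients) per group", the same rate in every arm.

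The primary endpoint is handled differently: SAP 7.3 and 15.1.3 specify MMRM with no imputation. The only named sensitivity analysis, in SAP 15.1.3, concerns outliers in the primary endpoint. None addresses missing CIC or Top 3 data.

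**The concern.** LOCF enters an early rating as if it had been observed at Week 24. For CIC the earliest candidate is the Day 14 rating (Protocol 12.2.2), taken less than a week after the Day 9 start of Dose Level 4 in Protocol Table 5. For Top 3 the scheduled candidates are Weeks 8 and 16.

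Two mechanisms can bias the Week 24 contrast:

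- **The treatment effect changes over time.** Carried values hold the effect at an earlier time. A growing effect is understated and a waning one overstated. An effect that plateaus before patients leave is not distorted.
- **Dropout is unequal and both arms share a time trend.** The arm that loses more patients is held nearer its early level, so a difference can appear with no true effect. It favours the arm with less dropout if the trend is improvement, and the arm with more dropout if it is worsening.

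At stake are the error rate and the estimates for two tests in the confirmatory sequence, and the sign of the CIC difference, which is one of the two win conditions. The plan contains nothing that would show whether either result depends on the imputation.

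**Working it through.** **1. The plan's own figures.** SAP 3.1 uses a difference of "10% (high dose sarizotan 20%, placebo 10"%), that is 10 points, with SD 12.5. The test is described as "using a two group t-test with a 0.050 two-sided significance level". The exact two-sample t calculation returns 34 per group (power 90.2%), as stated. The 43 enrolled equals 34 × 1.25 = 42.5, rounded up. A true 25% loss from 43 would leave 43 × 0.75 = 32.25, and 9 of 43 is 20.9%. These figures concern the primary endpoint only. No counterpart exists for CIC or Top 3.

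**2. Loss of a growing effect.** Assume that the effect rises linearly from zero to its full value at Week 24, with dropout d = 0.25 in each arm.

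Share kept = (1 − d) + d × f, where f is the mean time of the carried rating divided by 24 weeks. The share lost is d × (1 − f).

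*Carrying scheduled visits only, dropouts spread evenly over them:*
- CIC (Weeks 2, 8, 16): f = (26/3)/24 = 0.361, loss 0.25 × 0.639 = 16.0%. The range is 8.3% if all leave after Week 16 to 22.9% if all leave after Day 14.
- Top 3 (Weeks 8, 16): f = 12/24 = 0.50, loss 12.5% (range 8.3% to 16.7%).
- With 20.9% dropout the losses are 13.4% and 10.5%.

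*Allowing for attended early-discontinuation visits.* I applied the SAP 8.2 windows and closest-record rule. Leaving on Days 15–35 carries Day 14, Days 57–84 carries Day 56, and Days 113–140 carries Day 112. Otherwise the discontinuation-day rating is used. Departure is assumed uniform.
- CIC, leaving on Days 15–168: f = 0.504, loss 0.25 × 0.496 = 12.4%.
- Top 3, leaving on Days 57–168: f = 0.626, loss 0.25 × 0.374 = 9.3%.

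A simulation (43 per arm, 4,000 runs, correlation 0.6, dropout independent of outcome, scheduled visits only) with a true effect of 0.80 SD gave LOCF means of 0.67 (CIC visits) and 0.70 (Top 3 visits). The likelihood-based repeated-measures estimate gave 0.79 and 0.80.

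**3. False difference when there is no true effect.** Assume a shared linear trend of 0.8 SD by Week 24. This is borrowed from the planned placebo change on the primary endpoint, 10/12.5. Dropout of 35% versus 15% is also an assumption.

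Bias = trend × (difference in dropout) × (1 − f), with SE = √(2/43) = 0.216 SD.

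| Endpoint | Carried ratings | Bias (SD) | Two-sided error | Chance of the favoured sign |
|---|---|---|---|---|
| CIC | scheduled only | 0.8 × 0.20 × 0.639 = 0.102 | 7.6% | 68% |
| Top 3 | scheduled only | 0.8 × 0.20 × 0.50 = 0.080 | 6.6% | 64% |
| CIC | with discontinuation visits | 0.8 × 0.20 × 0.496 = 0.079 | 6.6% | 64% |
| Top 3 | with discontinuation visits | 0.8 × 0.20 × 0.374 = 0.060 | 5.9% | 61% |

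Error = Φ(−1.96 + z) + Φ(−1.96 − z) with z = bias/SE. For CIC in the first row, z = 0.474, giving 0.0686 + 0.0075 = 0.076. The nominal values are 5% and 50%.

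The simulated baseline-adjusted ANCOVA gave 7.2% for Top 3. For the CIC visits it gave 8.7%, but CIC has no baseline score to adjust for, so the unadjusted 7.6% is the closer figure. The likelihood estimate had essentially no bias (−0.01 to 0.00 SD).

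**4. When the false difference disappears.** With equal dropout or zero trend the formula gives exactly zero, and simulated rejection was 4.8% to 5.4%.

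**The case against.** The strongest case for leaving the plan alone has five parts.

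- **Discontinuation visits.** The schedule of events requires the Week 24 evaluations when a patient leaves early, so carried ratings are later than the last scheduled visit. This stands. It is why the losses are ranges and why the lower rows of the table are smaller. It reduces the bias without removing it.
- **Planned equality.** Attrition is assumed equal across arms and no time trend is documented for either endpoint. This stands: unequal dropout with a trend is a risk, not a feature of the plan.
- **Target.** Protocol 15.2.6 refers to CIC at Week 24/endpoint, which could mean status at the last assessment. The wording is ambiguous, and the SAP presents the result as Week 24.
- **Fair comparison.** The simulated dropout did not depend on outcome, which suits a likelihood method. This stands, and it is a reason to add a tipping-point analysis rather than a reason to keep LOCF.
- **Existing checks.** By-visit summaries are planned and Top 3 is tested only third. Both help, but neither tests the handling of dropouts.

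A reader might also infer that unequal dropout by itself produces a difference, or that LOCF could hand sarizotan a false win. The documents support neither. A time trend is also needed, and with an improving trend heavier dropout on sarizotan favours placebo. In the first row of the table the error would then split into 6.9% favouring placebo and 0.7% favouring sarizotan, against 2.5% each. The win rule also requires significance on the primary endpoint, which LOCF does not touch.

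**Conclusion.** The point holds as a limited one. LOCF is the sole specified handling of missing Week 24 data for two tests in the confirmatory sequence, in a trial that plans for 25% attrition and already uses a better method for its primary endpoint.

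Under the stated assumptions a linearly growing effect is understated by roughly 9–13% for Top 3 and 12–16% for CIC. With no true effect, a shared 0.8 SD trend and 35% versus 15% dropout, two-sided error is about 6.6–7.2% for Top 3 and 7.6% for CIC before allowing for discontinuation visits. The chance of a given CIC sign is then about 68% instead of 50%, in favour of the arm with less dropout if the trend is improvement.

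These figures rest on a linear course, dropout unrelated to outcome, CIC treated as continuous, and SD-scale inputs borrowed from the primary endpoint. The documents supply none of these for CIC or Top 3. Shrinkage alone does not reverse the expected CIC direction. It would be wrong to read this point as undermining the primary analysis.

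**What to change.** Make these changes before database lock and unblinding:

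- **Top 3 Concerns:** analyse change from baseline by MMRM at Weeks 8, 16 and 24, with treatment, visit, treatment-by-visit, baseline and age, unstructured covariance and Kenward-Roger degrees of freedom. Put the Week 24 high-dose contrast in the testing sequence. The score is continuous (0–300), so the form of the primary model carries over.
- **CIC:** multiply impute missing Week 24 ratings by sequential ordinal logistic regression on earlier ratings, treatment and age. Run the Van Elteren test in each imputed data set and combine the normalised statistics by Rubin's rules. State that the direction for the win rule is read from the combined estimate. The same imputed data sets can serve the responder model.
- **Sensitivity:** keep LOCF for both endpoints and add a delta-adjusted (tipping-point) analysis, since both new methods assume data missing at random.
- **Record:** enter the change in SAP 3.3, which now lists none.

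The cost is SAP wording and some programming. The drawback is a departure from the ANCOVA-LOCF that the protocol names for Top 3, which needs a short justification. The regulatory direction cited in SAP 15.1.4 concerns the win criteria, not the imputation method.

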15.2.3 ANALYSIS OF SECONDARY EFFICACY VARIABLES

15.2.3.1 Analysis of Caregiver Top 3 Concerns Total Score at Week 24

Descriptive statistics will be presented for actual value, change from baseline and percentage change from baseline in Top 3 Concerns total score by visit and treatment groups.

Document:	\\ieedc-vnasc01\BIOSdata\Newron\Sarizotan\PXA76395\Biostatistics\Documentation\SAP		
Author:	[name]	Version Number:	V2
		Version Date:	[30March2020]
Template No:	CS_TP_BS016 – Revision 4	Reference:	CS_WI_BS005
Effective Date:	01Apr2016		

Comparisons between treatments will be done using an ANCOVA model. The model will include treatment group and the baseline value along with age as covariates. Change will be estimated using the least-squares mean derived from the ANCOVA. Comparisons between treatment groups at Week 24 will be made using the difference in least-squares mean, 95% confidence interval (CI) and p-values from the ANCOVA model.

Additional summaries of the Top 3 Concerns will be presented as follows:

- i. Frequency and percentage of all Top 3 Concerns reported.
- ii. Mean change and percent change from baseline for each Top 3 Concern reported.
- iii. The number and percentage of patients with at least a 20% improvement in the Top 3 Concerns Total Score.

Additionally, graphical presentation will be provided.

15.2.3.2 Analysis of mean rating of Clinical Global Impression of Change (CGI-C) at Week 24

Summary statistics for the proportion of responders on the CGI - C (n, count, and percent) will be presented at all available scheduled visits for 24-week double-blind treatment period as per protocol.

Summary statistics will also be presented for the CGI-C mean change score and summarized by visit. Additionally, graphical presentation will be provided.

15.2.3.3 Analysis of change from baseline to Week 24 in Motor-Behavioral Assessment Scale (MBAS)

Descriptive statistics will be presented by treatment group for actual and change from baseline in Motor-Behavioral Assessment scale, both for subtotals and grand total at all available scheduled visits for the 24-week double-blind treatment period, as per protocol.

15.2.3.4 Analysis of change from baseline to Week 24 in other respiratory symptoms of RTT

Descriptive statistics will be presented by treatment group for actual values and change (or percent change) from baseline in other respiratory symptoms of RTT for both BioRadio™ and SOMNOtouch (*Refer to Section 15.2.1.4 for list of other respiratory symptoms*) at all available scheduled visits for the 24-week double-blind treatment period, as per protocol. Data from the Bio-Radio and the SOMNOtouch will not be pooled and will be analyzed separately.

Document:	\\ieedc-vnasc01\BIOSdata\Newron\Sarizotan\PXA76395\Biostatistics\Documentation\SAP		
Author:	[name]	Version Number:	V2
		Version Date:	[30March2020]
Template No:	CS_TP_BS016 – Revision 4	Reference:	CS_WI_BS005
Effective Date:	01Apr2016		

15.2.3.5 Analysis of change from baseline to Week 24 in Rett syndrome Clinical Severity Scale (RCSS)

Descriptive statistics will be presented by treatment group for actual score and change from baseline in the Rett syndrome Clinical Severity Scale (RCSS) at Week 24 of the double-blind treatment period, as per protocol.

15.2.4 EXPLORATORY VARIABLES & DERIVATIONS

Primary efficacy endpoint will also be analyzed for the group of patients who have Sarizotan threshold plasma concentration (>400 ng/ml) vs placebo. The analysis will be analyzed as described in Section 15.1.3. Additional analyses based on exposure and response will be performed.

16. QUALITY OF LIFE ANALYSIS

Not applicable.

17. SAFETY OUTCOMES

All outputs for safety outcomes will be based on the Safety population.

17.1. ADVERSE EVENTS

Adverse Events (AEs) are be coded using MedDRA central coding dictionary version 22.0.

An AE is defined as any untoward medical occurrence in a patient or clinical investigation patient administered a pharmaceutical product that does not necessarily have a causal relationship with the product. An AE can therefore be any unfavorable and unintended sign (including a new, clinically important abnormal laboratory finding), symptom, or disease, temporally associated with drug administration, whether or not related to the product.

The above definition covers also cases of

- Exacerbation of pre-existing diseases or conditions.
- Pre-existing diseases or conditions (reported at time of screening in medical history) will not be considered AEs unless there is an increase in the frequency or severity, or a change in the quality of the disease or condition.
- Events occurring in subjects treated with matching placebo are also considered AEs.

An AE will be defined as a treatment-emergent adverse event (TEAE) if the first onset (or

Document:	\\ieedc-vnasc01\BIOSdata\Newron\Sarizotan\PXA76395\Biostatistics\Documentation\SAP		
Author:	[name]	Version Number:	V2
		Version Date:	[30March2020]

Template No: CS_TP_BS016 – Revision 4
 Effective Date: 01Apr2016

Reference: CS_WI_BS005

worsening, in the case of pre-existing disease) is after the first administration of study treatment throughout the study. In addition, any serious adverse events (SAEs) reported in the 30 days following last dose of IMP will be recorded and counted in the final clinical study report.

See [Appendix 1](#) for handling of partial dates for AEs. In the case where it is not possible to define an AE as treatment emergent or not, the AE will be classified by the worst case; i.e. treatment emergent.

An overall summary of number of subjects within each of the categories described in the subsection below, will be provided as specified in the templates. Listings will include TEAEs and Non-TEAEs. Listings will be provided for TEAEs, SAE and TEAEs leading to discontinuation from study for safety analysis set.

